8.2 Serious Adverse Events

8.2.1 SAE Definitions

A Serious Adverse Event (SAE) is any untoward medical occurrence that at any dose:

- Results in death
- Is life threatening (defined as an event in which the subject was at risk of death at the time of the event; it does not refer to an event which hypothetically might have caused death if it were more severe)
- Requires inpatient hospitalization or causes prolongation of existing hospitalization
- Results in persistent or significant disability/incapacity
- Results in a congenital anomaly/birth defect
- Is an important medical event (defined as a medical event(s) that may not be immediately life-threatening or result in death or hospitalization but, based upon appropriate medical and scientific judgment, may jeopardize the subject or may require intervention [e.g., medical, surgical] to prevent one of the other serious outcomes listed in the definition above. (Examples of such events include, but are not limited to, intensive treatment in an emergency room or at home for allergic bronchospasm; blood dyscrasias or convulsions that do not result in hospitalization.) Potential drug induced liver injury (DILI) is also considered an important medical event.

Suspected transmission of an infectious agent (e.g., pathogenic or nonpathogenic) via the study drug is an SAE (e.g. contamination of drug product). Although pregnancy, overdose, new cancers, and potential drug induced liver injury (DILI) are not always serious by regulatory definition, these events must be handled as SAEs. Any component of a study endpoint that is considered related to study therapy (e.g., death is an endpoint, if death occurred due to anaphylaxis, anaphylaxis must be reported) should be reported as an SAE (see below for reporting details).

The following hospitalizations will not be considered SAEs in this study:

- A visit to the emergency room or other hospital department < 24 hours, that does not result in admission, unless otherwise deemed an important medical or life-threatening event
- Elective surgery, planned prior to signing study consent
- Admissions as per protocol for a planned medical/surgical procedure

- Routine health assessment requiring admission for baseline/trending of health status (e.g. routine colonoscopy)
- Medical/surgical admission not intended to remedy ill health and/or planned prior to entry into the study. Appropriate documentation is required in these cases
- Admission encountered for another life circumstance that carries no bearing on health status and requires no medical/surgical intervention (e.g., lack of housing, economic inadequacy, caregiver respite, family circumstances, administrative reason).

8.2.2 Serious Adverse Event Collection and Reporting

All events meeting the definition of a serious adverse event should be reported according to the departmental SAE checklist and SAE form. SAEs will be collected from a subject's first dose of study medication until 100 days after the last dose of study medication. The initial SAE form should be sent to the following within 24 business hours / 1 business day of the Principal Investigator becoming aware:

1. [name]: [contact]
2. [contact]
3. Local Institutional Review Board when reporting requirements are met.
4. SecuraBio, [contact] and [contact]

In addition to completing appropriate patient demographic and suspect medication information, the report should include as applicable the following information that is available at the time of report within the Sections B and C of the departmental SAE form:

- CTCAE term(s) and grade(s)
- current status of study drugs
- all interventions to address the AE (testing and result, treatment and response)
- hospitalization and/or discharge dates
- event relationship to study drug

Follow-up reports:

Additional information may be added to a previously submitted report by adding to the original departmental SAE form and submitting it as follow-up or by creating supplemental summary information and submitting it as follow-up along with a copy of the original departmental SAE form.

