Main Inclusion and Exclusion Criteria	
Inclusion criteria: Men and women 18 years of age or older with unresectable stage III or stage IV melanoma by AJCC 8th edition who have progressed on anti-PD1 therapy after a minimum of 12 weeks of therapy.
 
Exclusion criteria: Patients with known or suspected symptomatic or progressive CNS metastases; patients with treated CNS disease who are stable on repeat imaging at 2-4 weeks post SRS and neurologically stable are allowed. Patients with active autoimmune disease requiring treatment and patients with uveal or mucosal melanoma are not eligible. Patients with uncontrolled cardiovascular, pulmonary, and certain infectious disease are also excluded.

Investigational Product	
Duvelisib is an oral medication that will be administered in doses from 15mg once a day to 25mg BID for dose finding studies.
 
Nivolumab is supplied as a 240mg/24 mL formulation to be administered as an IV infusion at 240mg every 2 weeks, and if tolerated, potentially changed to 480mg once every 4 weeks.

Duration of administration	Both duvelisib and nivolumab will be administered in 4-week cycles until progression of disease, unacceptable toxicity, or 1 year, whichever is longer.
Reference therapy	For patients who have progressed on immunotherapy and targeted agents, there is no current standard of care ¹ and clinical trials are the recommended option.
Correlative studies	Patients will have peripheral blood draw and tumor biopsy performed at baseline and after 12 weeks of treatment in both phases of the trial. For the phase I cohort, changes in immune cell populations, particularly CD8+ T cell proliferation, will be used to measure the immunomodulatory effect of increasing doses of duvelisib. Additional studies are planned to characterize T cell phenotype, function, and metabolism as well to evaluate expression of genes involved in autoimmunity and inflammation and to correlate with toxicity. Correlative studies will be used along with toxicity data to inform the phase II dose. Ideally, the dose chosen will have a potent anti-tumor immune profile such as high CD8+ T effector cells, low T regulatory cells, low myeloid-derived suppressor cells.

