3.2.2 Secondary Endpoints

Several secondary endpoints will be analyzed as follows:

- Acute and late toxicities rates throughout treatment, as graded by CTCAE v5.0 in patients at each dosing interval and in the expansion cohort
- Clinical benefit of combination therapy, defined as complete response, partial response and stable disease as assessed by RECIST v1.1, initially assessed at 12 weeks after initiation of therapy and subsequently at 12-week intervals until progression

- Duration of response defined by time at which measurement criteria are first met for complete response or partial response until the first time at which progressive disease is objectively documented
- Progression-free survival defined as time at start of treatment and first date of documented progression or death due to any cause
- Overall Survival defined as the time of start of treatment and the date of death due to any cause. Patients who are alive will be censored at the time of the last follow-up. Patients will be followed for survival for 5 years.
- Safety of the combination of anti-PD1 and duvelisib measured by adverse events graded by CTCAE v5.0. Adverse events will be captured during treatment and 100 days after discontinuing treatment. We will continuously monitor for DLTs as defined in section 8.1 that are possibly, probably or definitely related to treatment. If the adverse event rate exceeds acceptable limits, the study will be modified or discontinued.
- Subset analysis will be performed to determine how certain disease characteristics affect response to the combination, including prior time prior to progression while on anti-PD1 therapy, presence of CNS disease, radiated CNS disease and tumor BRAF mutation status.

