5.2 Screening and Pretreatment Evaluations

Screening and pretreatment evaluation will take place within 28 days from study initiation. The evaluation includes the assessments in the table below

Table 5.2 Screening and Pretreatment Evaluations

Evaluation	Description
Informed consent	A subject is only considered enrolled when an IRB/IEC approved informed consent form is signed and dated.
Medical Record Review	The patient will be interviewed and medical history will be reviewed in the EMR. Details of risk factors for potential events such as pulmonary or infectious complications should be evaluated. Toxicities from prior treatments and allergies will also be reviewed.
Inclusion/exclusion criteria	Criteria will be reviewed as well as compared with the medical record.
Pre-treatment tumor biopsy	Should be performed within 4 weeks of treatment, see laboratory manual for further details.

Vital signs	Includes height (at screening only), weight, blood pressure, temperature, heart rate, oxygen saturation, respirations, body mass index (at screening only).
Physical Examination	Physical exam should be performed at screening and within 3 days of treatment initiation.
Performance status	ECOG performance status will be evaluated and recorded.
Laboratory tests	See section 6.4 for tests to be performed at screening and at time of drug initiation. Labs are performed locally and may be collected within 3 days prior to dosing.
Pregnancy test	Urine or serum pregnancy test should be performed in all WCBP prior to study initiation.
Contraceptive use	Men and women will be evaluated for and counseled about highly effective contraceptive use.
Concomitant medications	Medication review will take place at screening and at each subsequent visit.
Assessment of signs and symptoms	Evaluation will be performed at screening and at each subsequent visit.
Monitor for adverse events	AEs are collected from the start of treatment including SAEs.
Diagnostic imaging	CT with contrast is the preferred modality and should include chest/abdomen/pelvis as well as other body areas based on the patients' disease. CT without contrast or MRI is also permitted.
Brain imaging	For patients with a history of brain metastases or concerning symptoms, brain imaging should be performed within 4 weeks of treatment. Brain MRI is preferred, but CT is also permitted. Brain MRI/CT will be required for all patients at screening.

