8.4 Nonserious Adverse Events

A nonserious adverse event is an AE not classified as serious. The collection of non-serious AE information should begin upon initiation of study drugs. All non-serious adverse events (not only those deemed to be treatment-related) should be collected continuously during the treatment period and for a minimum of 100 days following the last dose of study treatment.

Non-serious AEs should be followed to resolution or stabilization, and/or reported as SAEs if they become serious. Follow-up is also required for non-serious AEs that cause interruption or discontinuation of study drug and for those present at the end of study treatment, as appropriate.

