13.2 Phase II Correlative Studies

Patients enrolled in the phase II cohort will have blood draws at baseline and 12 weeks on treatment. Tumor biopsies will be performed at baseline and after 12 weeks on treatment. For the phase II correlative studies, we will use a multi-level approach to evaluate the interplay of the immune system with the tumor microenvironment (pre-treatment, post-treatment with duvelisib, and at progression). Studies will be focused on answering several questions pertinent to the mechanism of action of duvelisib and resistance to PD1 therapy.

First, we will characterize T cell responses to duvelisib. In combination with data from flow cytometry in Phase I studies, and we will add more detailed studies to characterize T cell activation through functional assays. We will also use Cytek to evaluate markers of T cell exhaustion, including LAG3, TIM3, TIGIT, CD38, bcl2 and HLA-DR. This data will be corroborated with a Nanostring T cell characterization panel which evaluates RNA expression of pathways involved in T cell activation, exhaustion, persistence, and metabolism. T cell metabolism will also be evaluated by an assay for mitochondrial mass.

Second, we will evaluate changes in the tumor microenvironment while on duvelisib using tumor biopsy samples. We will use flow cytometry to evaluate immune populations within tissues and evaluate whether these reflect changes in the periphery. Multispectral immunofluorescence will be used to evaluate the spatial relationship and interplay between immune populations, particularly between pro-inflammatory and anti-inflammatory populations. Presence and alterations of B cells in biopsy samples are of particular interest, given the known activity of duvelisib on B cells and the prognostic implications of B cells and tertiary lymphoid structures.

Finally, global changes in the tumor microenvironment will be evaluated by single cell RNAseq. For these studies, fresh tissue from 9 patient's tumors with matched peripheral blood samples will be used. In addition to providing important data regarding alterations associated with duvelisib, these samples will also be informative regarding acquired resistance to anti-PD1 therapy.

The following techniques will be used:

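### AE and SAE collection starts at first dose, so complications of the required baseline research biopsy that arise before dosing are not systematically collected

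*Combined protocol and SAP*

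**What the plan says.** **Start of collection.** Four places in the protocol agree:

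- Section 8.2.2, for SAEs: from the "first dose of study medication until 100 days after the last dose of study medication".
- Section 8.4: "The collection of non-serious AE information should begin upon initiation of study drugs".
- Table 5.2: "AEs are collected from the start of treatment including SAEs".
- Section 3.2.2, for the safety endpoint: "Adverse events will be captured during treatment and 100 days after discontinuing treatment".

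In Table 6.7.1 the row for adverse events and unanticipated problems is blank at Screening and begins at Visit 1.

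**Baseline biopsy.** The Protocol Summary states: "Patients will have peripheral blood draw and tumor biopsy performed at baseline and after 12 weeks of treatment in both phases of the trial". Section 13.1 repeats this for phase I, and Section 13.2 for phase II: "Tumor biopsies will be performed at baseline and after 12 weeks on treatment". No opt-out or archival-tissue alternative is given. Table 5.2 lists it as a pre-treatment evaluation and says of its timing: "Should be performed within 4 weeks of treatment, see laboratory manual for further details". Table 6.7.1 places the first biopsy mark under Visit 1, not Screening.

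**The concern.** The baseline biopsy is invasive and is done for the study's correlative work. A bleed, pneumothorax or infection arising from it before the first dose is a harm caused by taking part in the trial, but it occurs before any adverse-event form is due. The case of most concern is a complication that keeps the patient from starting treatment, because no later visit then exists at which collection would begin. The week-12 biopsy falls inside the collection window, so the two biopsies that the protocol requires are handled differently. At stake are the protection of participants and a complete account of what the study procedures cost them. The estimate of treatment effect is not at stake.

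**Working it through.** There is no figure in the plan to reproduce. The check sets the time windows side by side.

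1. **Entry to the study.** Table 5.2 counts a subject as enrolled at signed consent. Section 3.1.2 allows 28 days from consent to the start of treatment.
2. **Biopsy.** Under Table 5.2 it may be done up to 4 weeks before treatment, and 4 × 7 = 28 days. I take it to follow consent, since it is a study procedure.
3. **Collection.** It opens at first dose for SAEs (Section 8.2.2) and at start of study drugs for non-serious AEs (Section 8.4). Table 5.2 and Section 3.2.2 agree.
4. **Gap.** The interval with no AE or SAE collection runs from the biopsy to the first dose. It lasts at most 28 days under Table 5.2. If the biopsy is done at Visit 1, as Table 6.7.1 suggests, the gap is shorter. A baseline sample still has to precede the first dose, so the gap does not close.
5. **Events that fall in the gap.** An event whose onset follows the first dose is collected, whatever its cause. An event that begins earlier and worsens after dosing is also collected, because Section 8.0 counts worsening of an existing condition. What is left out is an event that arises before dosing and does not worsen afterwards, and any event in a patient who is never dosed.
6. **The protocol's own definition.** Section 8.0 ties an adverse event to participation in the study, whether or not it is related to the drug. A pre-dose biopsy complication in an enrolled subject meets that definition. The definition is therefore wider than the collection window.
7. **Reporting to the IRB.** Section 9.6 covers serious, unexpected events associated with the drug or the study treatment. A complication of a study procedure before treatment does not clearly qualify.
8. **Possible rescue text.** Section 9.7 asks for significant worsening to be recorded, but it refers to interim or final examinations and does not override the stated start dates. Section 10.1 has the monitoring board discuss subject safety issues and unanticipated problems, and commits to IRB policy on the latter. That is a reporting route, not data collection.
9. **Effect on the analysis.** Section 14.2.1 restricts the safety population to patients who received some of the regimen. The DLT window in Section 8.1 opens at the first combined dose, and Section 14.2.3.4 counts only events with at least a possible relation to treatment. A pre-dose biopsy event enters none of these, so no endpoint, DLT count or stopping boundary changes.

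**The case against.** The strongest reply has four parts.

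*Such events would be seen anyway.* Table 5.2 assesses signs and symptoms at screening and requires a physical examination within 3 days of treatment initiation. Section 4.2.3 requires adequate recovery from complications before therapy. The routes in Section 10.1 are not limited to dosed patients. This stands in part. A reader might infer that these complications go wholly unobserved, or that the monitoring bodies and the IRB would receive nothing about them. The documents do not support that. They support only the narrower statement that the events are not systematically collected as AEs or SAEs.

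*The schedule puts the biopsy at Visit 1, in a column that has an adverse-event mark.* This shows that the documents disagree on timing and that 4 weeks is an outer limit. It shortens the gap without removing it.

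*First dose is a sensible start for drug toxicity, and an exposure-based safety population suits a toxicity analysis.* Both are correct. A reader might infer that the safety population is defective because it leaves out patients harmed before dosing. It is not: it is defined for a different purpose, and it should stay as it is.

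*Instructions on procedure events may sit in the laboratory manual, the departmental SAE checklist or IRB policy.* They may, but nothing in the protocol says so. The protocol's explicit start dates would still conflict with any such instruction.

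**Conclusion.** The concern holds in a limited form. Followed exactly, the plan does not systematically collect AEs or SAEs that arise between the required baseline biopsy and the first dose, although its own definition counts them as adverse events. The gap is up to 28 days per patient under Table 5.2. It concerns the baseline biopsy only, in a study planned for up to 42 patients.

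The number of missed events cannot be derived from the documents. A reader might assume a serious complication rate of 1% to 5% and obtain 42 × 0.01 = 0.42 to 42 × 0.05 = 2.1 expected events, and a chance of at least one of 1 − 0.99^42 = 0.34 to 1 − 0.95^42 = 0.88. That range should not be relied on. The documents give no complication rate, and eligible lesions extend to superficial nodules and palpable nodes (Sections 4.1 and 12.2), where the risk may differ from that of deep organs. The calculation also takes every event to occur before dosing and to go unrecorded by any other route.

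The conclusion rests on the stated windows and on the biopsy following consent. It is a participant-safety and reporting matter that should be corrected, and it does not bear on the trial's efficacy or toxicity conclusions.

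**What to change.** - In Sections 3.2.2, 5.2, 8.2.2 and 8.4, collect SAEs, and any AE related to a protocol-mandated procedure, from signed consent. Keep first dose as the start for all other AEs. Add the matching Screening mark in Table 6.7.1.
- Extend the IRB reporting criterion in Section 9.6 to events associated with study procedures. Without this, a biopsy SAE would be collected but would still not clearly be reportable there. Bring the parallel sentence in Section 10.1 into line.
- Reconcile the timing of the baseline biopsy between Tables 5.2 and 6.7.1.
- List pre-dose procedure events separately from events on treatment, and leave the safety population in Section 14.2.1 unchanged.

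Starting all SAEs at consent, and not only those linked to the biopsy, avoids a causality judgement before the event is recorded. It would also cover serious reactions to the prophylaxis that Section 6.8 requires before duvelisib.

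The cost is wording in a few sections, one schedule mark, and a small amount of extra data entry and reporting during screening. Sample size, stopping boundaries and analyses stay the same.

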8.4 Nonserious Adverse Events

A nonserious adverse event is an AE not classified as serious. The collection of non-serious AE information should begin upon initiation of study drugs. All non-serious adverse events (not only those deemed to be treatment-related) should be collected continuously during the treatment period and for a minimum of 100 days following the last dose of study treatment.

Non-serious AEs should be followed to resolution or stabilization, and/or reported as SAEs if they become serious. Follow-up is also required for non-serious AEs that cause interruption or discontinuation of study drug and for those present at the end of study treatment, as appropriate.

8.5 Laboratory Test Result Abnormalities

The following laboratory test result abnormalities should be captured on the nonserious AE Case Report Form (CRF) page or SAE Report Form (paper or electronic) as appropriate:

- Any laboratory test result that is clinically significant or meets the definition of an SAE
- Any laboratory test result abnormality that required the subject to have study drug discontinued or interrupted
- Any laboratory test result abnormality that required the subject to receive specific corrective therapy.

It is expected that whenever possible, the clinical rather than laboratory term will be used by the reporting investigator (e.g., anemia versus low hemoglobin value).

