6.4 Laboratory Evaluations

Blood sampling will be performed with the laboratory tests below at each visit, with exceptions noted below:

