Neutropenia	Absolute neutrophil count (ANC) 500 to 1000 cells/µL	
Duvelisib
 
 - Maintain duvelisib dose - Monitor ANC at least weekly 
Nivolumab
 
 - Withhold nivolumab until resolved if it is felt to contribute to the neutropenia, and otherwise continue nivolumab as previously - Resume at same dose
	ANC less than 500 cells/µL	
Duvelisib
 
 - Withhold duvelisib

Toxicity	Adverse Reaction Grade	Recommended Management
		
 - Monitor ANC until > 500 cell/uL - Resume duvelisib at same dose (first occurrence) or at a reduced dose for subsequent occurrence 
Nivolumab
 
 - Withhold nivolumab until resolved if it is felt to contribute to the neutropenia, and otherwise continue nivolumab as previously - Resume at same dose 
*If concern for auto-immune neutropenia, then hold nivolumab and follow practice guidelines

Thrombocytopenia	Platelet count 25K to < 50K cells/ μ L (Grade 3) with Grade 1 bleeding	
Duvelisib
 
 - No change in dose - Monitor platelet counts at least weekly 
Nivolumab
 
 - Withhold nivolumab until resolved - Resume at same dose
	Platelet count 25K to < 50K cells/ μ L with grade 2 bleeding OR platelet count <25K cells/ μ L (Grade 4)	
Duvelisib
 
 - Withhold duvelisib - Monitor platelet count until > 25K cells/uL and resolution of bleeding if applicable. - Resume duvelisib at same dose (first occurrence) or resume at a reduced dose for subsequent occurrence 
Nivolumab
 
 - Withhold nivolumab until resolved - Resume at same dose 
*If concerned for autoimmune thrombocytopenia, hold nivolumab and follow practice guidelines

Table 7.7 Dose Reductions for Duvelisib

Initial Dose	Decreased Dose
15mg Daily	None

25mg Daily	15mg Daily
25mg BID	25mg Daily

Note: If patient is on dose level 1, 15mg daily and has a dose interruption, duvelisib will be resumed at same dose. If patient subsequently requires another dose interruption at this level for the same toxicity, duvelisib should be discontinued. No more than 2 dose reductions for the same side effect are allowed for any patient, irrespective of starting dose.

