8.1 Dose Limiting Toxicities

Acute dose limiting toxicities (DLTs) are defined as any of the following AEs and laboratory abnormalities considered possibly, probably, or definitely related to study treatment that occur any time from the initial dose of duvelisib in combination with nivolumab through day 28 of treatment. Toxicities occurring from day 29 through 28 days after completion of treatment will be considered late toxicities. Only acute DLTs will be considered for decisions to continue enrollment at the current dose level or proceed to the next dose level. Acute and late toxicities will be considered when deciding on the RP2D and will be discussed in monthly Data Safety Monitoring Board (DSMB) meetings. See Section 15.0 for further details.

Severity of adverse events will be graded by National Cancer Institute Common Terminology Criteria for Adverse Events version 5.0 (CTCAE v5.0). A goal of $\leq 33\%$ DLTs at each dose level will be considered acceptable.

Whenever possible, biopsies are recommended if they can be done safely to help determine between immune-related and other etiologies of toxicity, particularly for rash and colitis. Biopsies for elevated liver enzymes and/or for pneumonitis should be considered if deemed feasible and safe in the context of risk:benefit evaluation. General criteria for consideration of biopsy:

- Diarrhea/colitis
 - Biopsy proven grade ≥ 3 immune-related colitis
 - Diarrhea of grade ≥ 3 that does not respond to treatment with steroids within 5 days
- Pneumonitis
 - Immune-related pneumonitis grade ≥ 2

- Any grade ≥ 3 pneumonitis
- Hematologic abnormalities
 - Neutropenia grade 4 despite holding duvelisib for 7 days
 - Thrombocytopenia grade ≥ 3 with bleeding
 - Thrombocytopenia grade 4
- Other immune-related toxicities
 - Any grade ≥ 3 toxicity that does not respond to treatment within 5d
- For the remainder of non-hematologic toxicities, grade ≥ 3

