11.5 Neutropenia

Patients with hematologic conditions treated with duvelisib frequently developed neutropenia. CBC with differential should be checked at least every 2 weeks during cycle 1, and more frequently for those with ANC < 1000 cells/ μ L. Withhold duvelisib if ANC < 500 cells/ μ L, monitor weekly and resume at same dose of the first occurrence or at a decreased dose for subsequent occurrence. Duvelisib can be resumed when ANC > 100 is reached in the absence of signs of infection. G-CSF may be used per ASCO guidelines.

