14.2.3.3. Stopping Rule for Excessive Toxicity

We will use a Bayesian monitoring scheme to continuously monitor the dose limiting toxicity rate of the study combination at 30%. The DLT is defined generally as grade 3 and 4 toxicity, see section 8.1 for more detailed definitions. Again, a non-informative prior of Beta (0.5, 0.5) for the DLT rate will be used. We will hold patient recruitment if the posterior probability $\text{Pr}(\text{SAE rate} > 30\%) \leq 0.7$, and the study committee and the PI will then decide whether to modify or discontinue the study. The stopping boundary for toxicity is given in the following table:

Number of SAEs \geq	in Number of Patients =
2	3-5
3	6-7
4	8-10
5	11-13
6	14-16
7	17-19
8	20-22
9	23-26
10	27-29
11	30

We simulate the operating characteristics under various assumed true toxicity rates (see the following table):

Scenario	Prob.Of.Tox	Prob.Early.Stop
1	0.1	0.0885
2	0.2	0.3332
3	0.3	0.6727
4	0.4	0.9128

14.2.3.4. Analysis of Safety (for both the phase I portion and the phase II portion)

We will consider a toxicity event to be an adverse event (evaluated by CTCAE 5.0) that is possibly, probably, or definitely related to treatment. Toxicity will be considered attributable to both study drugs, unless investigator determines one of the drugs is a more likely culprit (e.g. CMV due duvelisib). The maximum grade of toxicity for each category of interest will be recorded for each patient and the summary results will be tabulated by category and grade. These will also be done for early toxicities (within 4 weeks) and late toxicities (after 4 weeks) separately.

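### Section 8.5 has no CTCAE-grade trigger for recording laboratory abnormalities, so some grade 3 values can be left out of the safety tables at the investigator's discretion

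*Combined protocol and SAP*

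**What the plan says.** Section 6.4 collects the data: "Blood sampling will be performed with the laboratory tests below at each visit, with exceptions noted below". Table 6.4.1 includes platelets, WBC with differential, chemistries and liver tests.

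Section 8.5 says which abnormalities go on the AE or SAE form. Its first entry is "Any laboratory test result that is clinically significant or meets the definition of an SAE". The second covers abnormalities that led to a pause or stop of study drug, and the third those that had to be treated.

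Section 7.0 counts both duvelisib and nivolumab as study drugs, so a hold of either meets the second entry.

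Section 14.2.3.4 defines a toxicity event as an adverse event at least possibly related to treatment. It then plans: "The maximum grade of toxicity for each category of interest will be recorded for each patient". Results are tabulated by category and grade, and separately for early and late toxicities. No analysis of the laboratory values themselves is planned.

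On neutropenia, section 11.5 says: "Patients with hematologic conditions treated with duvelisib frequently developed neutropenia". For ANC 500-1000, Table 7.6 keeps the duvelisib dose, asks for at least weekly counts, and says of nivolumab: "Withhold nivolumab until resolved if it is felt to contribute to the neutropenia, and otherwise continue nivolumab as previously".

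**The concern.** Toxicity graded by CTCAE v5.0 is a secondary endpoint at each dose level and in the expansion cohort (section 3.2.2). Acute and late toxicities also feed the choice of RP2D (sections 8.1 and 14.1.1). A graded laboratory toxicity rate should follow from the values measured. Here a value reaches the table only by first becoming an adverse event, and for some grade 3 values that can rest on one undefined judgement made open-label. Two investigators could both follow the plan and report different grade 3 rates from the same blood counts. When a value is lost this way, the reported rate falls.

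**Working it through.** The plan states no figure to reproduce. The check is to take each type of abnormality through Table 7.6 and then through section 8.5, assuming Table 7.6 is followed.

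| Abnormality | Action in Table 7.6 | Route into the AE form under 8.5 |
|---|---|---|
| ALT/AST 3 to 5 x ULN (grade 2) | Duvelisib kept, nivolumab withheld | Interruption: captured |
| ALT/AST above 5 x ULN (grades 3 and 4) | Duvelisib withheld or discontinued, nivolumab permanently discontinued | Captured |
| Platelets 25K to <50K (grade 3), grade 1 bleeding | Duvelisib kept, nivolumab withheld | Interruption: captured |
| Platelets 25K to <50K with grade 2 bleeding, or <25K | Both withheld | Captured |
| ANC below 500 | Duvelisib withheld | Captured |
| ANC 500-1000, asymptomatic, nivolumab continued, untreated | Duvelisib kept, more frequent counts | Clinical-significance judgement only |
| Platelets 25K to <50K, no bleeding, no hold or treatment | No row | Clinical-significance judgement only |
| Grade 3 chemistry value with no row, no hold or treatment | No row | Clinical-significance judgement only |

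The last three rows are the gap. A nivolumab hold, or growth factor given as treatment, would bring an ANC of 500-1000 back in. The neutropenia rows print no grade. Reading 500-1000 as grade 3 relies on the CTCAE v5.0 cut-points, which the protocol adopts but does not reprint.

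Other sections do not close the gap. Section 8.0 defines an adverse event broadly, 8.4 collects all non-serious adverse events, 9.7 records significant worsening, and 10.1 evaluates all toxicities by the CTC version 5.0. None says that a laboratory value becomes an adverse event at a given grade. The potential liver injury rule in 8.8 is objective but needs transaminase and bilirubin elevation together.

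**Size.** The documents give no neutropenia rate for this combination. One omitted event changes a dose level of 6 patients by 1/6 = 17 percentage points, and the phase II cohort of 30 by 1/30 = 3.3 points.

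For illustration only, let a be the share of patients with worst ANC 500-1000 and b the share below 500. If no patient in the first group is recorded, the captured share of both groups together is b/(a+b). Assume a = 10-30% and b = 5-15%:
- a = 10%, b = 5%: 5/15 = 33%
- a = 30%, b = 15%: 15/45 = 33%
- a = 10%, b = 15%: 15/25 = 60%
- a = 30%, b = 5%: 5/35 = 14%

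If every such value is judged significant, the captured share is 100%. These are assumptions, not estimates for this trial.

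**The case against.** The case against has real force.

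- Section 8.5 lists what should be captured and is not worded as exclusive. Table 7.6 places ANC 500-1000 among hematologic adverse reactions and orders weekly counts, so many investigators would call it significant. That stands: such events may well be reported. But the plan does not require it.
- Laboratory results are source data under section 10.2, so an under-count could be repaired at reporting. That also stands, but no planned analysis uses those values.
- The frequent neutropenia in section 11.5 refers to patients with hematologic conditions, and section 15.0 expects fewer toxicities in melanoma. This bears on how often the gap would matter, not on whether it exists.

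A reader might also draw four stronger inferences that the documents do not support.

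- *Liver tests and blood counts in general escape capture.* They do not: the drug holds in Table 7.6 bring in most of them.
- *Section 8.5 is narrower than the DLT rule it feeds.* Section 8.1 counts "any of the following AEs and laboratory abnormalities considered possibly, probably, or definitely related to study treatment" directly, and nothing routes DLT ascertainment through 8.5.
- *Missed grade 3 neutropenia distorts escalation or the phase II toxicity stopping rule.* The 8.1 list names only grade 4 neutropenia despite a 7-day hold. Section 14.2.3.3 describes DLT generally as grade 3 and 4 toxicity, but refers to 8.1 for the definition and tabulates SAEs. That inconsistency needs reconciling in its own right. So does the placing of the 8.1 list under a sentence about biopsy.
- *Reported rates would be about one third of the truth.* That figure appears only when the assumed ranges are paired low with low or high with high; crossing them gives 14% to 60%.

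**Conclusion.** The point holds in limited form. Recording has no grade trigger, and the three kinds of value in the last rows of the trace can be omitted by an investigator who follows the plan. The CTCAE-graded secondary safety endpoint, and the toxicity evidence for the RP2D, can therefore be understated. The extent cannot be computed from the documents and could be nil if investigators record these values anyway. The primary efficacy endpoint is untouched, and escalation for neutropenia is unaffected under the 8.1 list. The conclusion assumes that Table 7.6 is followed, that CTCAE v5.0 cut-points apply to ANC, and that the value is asymptomatic and untreated with both drugs continued. This is an inexpensive improvement worth making, not a defect in the trial's main inference.

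**What to change.** In section 14.2.3.4, add a table of the worst post-baseline CTCAE v5.0 grade per patient, derived from all protocol laboratory values whether or not an adverse event was reported or attributed to treatment. Show it as shift from baseline grade, by dose level and for the phase II cohort, for weeks 0-4 and after week 4.

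In section 8.5, add that any new grade 3 or higher laboratory value is recorded on the AE form regardless of judged significance.

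The cost is one paragraph, one bullet and one additional table from tests already drawn. No new test is needed. The downside is some extra AE and laboratory data entry, and slightly higher reported toxicity rates. Both changes concern reporting only; no change to dosing or clinical management is proposed.
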